#### 6. INVESTIGATIONAL PLAN

#### 6.1. Description of Overall Study Design and Plan

[figure not shown]
This Phase 2, multicenter, open-label, randomized, controlled clinical study is designed to evaluate the safety and efficacy of pegcetacoplan in patients who have post-transplant recurrence of C3G or IC-MPGN. There will be up to 12 subjects enrolled in this study. There are 3 main periods of this study for Part A, the core study.

[figure not shown]
- Screening period: an up to 8-week screening period, during which the screening renal allograft biopsy will occur
- Main period: a 52-week study period that contains 2 portions (controlled and noncontrolled) during which subjects will be randomized to either Group 1 or Group 2 at the Week 1 visit:
  - Controlled portion: Weeks 1-12 of the study
    - Group 1: Up to 9 subjects will be randomized to this treatment group and will receive pegcetacoplan treatment throughout the entire study; biopsies will occur at Week 12
    - Group 2: Up to 3 subjects will be randomized to this treatment group and will not receive pegcetacoplan treatment during the controlled portion; biopsies will occur at Week 12
  - Noncontrolled portion: Weeks 13-52 of the study
    - Group 1: Subjects will continue to receive pegcetacoplan treatment; biopsies will occur at Week 52
    - Group 2: Subjects will receive pegcetacoplan treatment following their
       Week 12 renal allograft biopsies; biopsies will occur at Week 52
- · Follow-up period: an 8-week follow-up period

Any subject who, in the opinion of the investigator, is experiencing clinical benefit from pegcetacoplan administration may participate in Part B, a long-term extension, in order to continue to receive treatment with pegcetacoplan until it is commercially available for the disease under study. If invited to participate, the subject can enter Part B as soon as his/her 52-week treatment period has ended and does not need to participate in the 8-week follow-up period. See the appendices (Section 15) for details about Part B.

Figure 1 presents the study design.

Figure 1: Study Design

Abbreviation: R = randomization.

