Urine pregnancy test		X	X	X	X	X	X	X	X	X	X	X	X	X	X	X	X	X	X
FSH, HIV, HCV, HBsAg, HBcAb R	х																		
AEs	Х	X	х	Х	Х	Х	X	X	Х	Х	Х	X	Х	X	X	X	X	X	X
Post-transplant immunosuppression plan documentation		x																	
Ophthalmologic evaluation (optional) S		XS													XS				

Abbreviations: ADA = antidrug antibodies; AE = adverse events;  $\beta$ -HCG =  $\beta$ -human chorionic gonadotropin; CDC = Centers for Disease Control and Prevention;

NOTE: When multiple assessments/procedures occur at the same time, order should be: vital signs, ECGs, blood collection/sampling, pegcetacoplan dosing.

CKD-EPI = Chronic Kidney Disease-Epidemiology Collaboration; ECG = electrocardiogram; eGFR = estimated glomerular filtration rate;

FSH = follicle-stimulating hormone; GFR = glomerular filtration rate; HBcAb = hepatitis B core antibody; HBsAg = hepatitis B surface antigen;

HCV = hepatitis C; N/A = not applicable; PK = pharmacokinetic(s); RBC = red blood cell; SC = subcutaneous;

SD-OCT = spectral domain optical coherence tomography.

A. Subjects who meet the medical history requirements will enter the screening period at Visit 1 and return for Visit 2, but all Visit 2 assessments need not occur in a single visit and Visit 2 can be split into multiple visits (eg, 2a, 2b).

- B. Subjects will self-administer SC pegcetacoplan after receiving appropriate training and sign-off by a research nurse or other personnel in their first treatment week. During site visits subjects will self-administer pegcetacoplan at the site, with the exception of the very first dose. Group 2 subjects will be trained on self-administration of pegcetacoplan and receive their supply of pegcetacoplan at the next scheduled clinic visit (Visit 7 or 8) following their biopsies.
- C. Visit 2 must occur at least 7 days after Visit 1 and at least 14 days prior to the Day 1 dosing date; the vaccinations and biopsy can occur any time after confirmation of eligibility based on Visit 1 data.
- D. Specific inclusion/exclusion criteria will be measured during screening, and some of them require confirmation prior to any activities of Day 1. See the inclusion/exclusion criteria in Section 7 for further detail.

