- E. Vaccinations against N. meningitidis, S. pneumoniae, and H. influenzae are mandatory, unless documented evidence exists that subjects have received all recommended vaccines or are nonresponders to vaccination. Any required vaccines should be administered during screening (Day -14), and any required boosters should be administered at Visit 6 (Day 56), unless an alternative vaccination schedule has been agreed with the medical monitor, as described in Section 9.1.4. Subjects who withdraw from the study prior to a scheduled vaccine booster, as recommended by the current Advisory Committee on Immunization Practices adult immunization schedule, will be offered the opportunity to return to the site to receive the booster. Vaccination serum samples (for antibody titer) will be collected prior to subject receiving vaccinations on that study visit.
- F. Full physical examination will only be performed at Study Weeks -4, 1, and 52. Brief physical examinations will be conducted at all other clinic visits, as noted. A symptom-driven physical examination may be performed at other times, at the investigator's discretion. Body height (cm) will be measured during screening only and weight (kg) will be measured throughout study, during brief and full physical examinations. Edema should be assessed at every visit.
- G. Week 12 biopsy must occur at a time point between Weeks 12 and 14, inclusive; Group 2 subjects cannot begin pegcetacoplan administration until after the biopsy occurs. Week 52 biopsy must occur at a time point between Weeks 48 and 52, inclusive, but after completion of the 24-hour urine collection scheduled for Week 48.
- H. Between site visits, subjects will be instructed to report any infusion site reaction to the study staff. Pump use safety assessment will be performed by licensed health care professional (ie, investigator or nurse) within 30 minutes following study drug administration at all clinic visits and during at-home qualification. See Manual of Procedures for more details.

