# 11.2. Recording and Reporting Adverse Events

AEs and SAEs will be collected from the signing of the informed consent form (ICF) until the exit/early termination visit.

All SAEs will be followed until satisfactory resolution, until baseline level is reached, or until the SAE is considered by the investigator to be chronic or the subject is stable, as appropriate.

All SAEs that are suspected of being related to study treatment must be reported immediately to the sponsor if the investigator becomes aware of them, regardless of the time since the completion of the clinical trial.

Any events that occur prior to the start of dosing will be categorized as pretreatment events; events occurring after the start of dosing will be recorded as TEAEs (the start date of dosing and, therefore, categorization of the event will be dependent on randomization assignment).

For each AE, the investigator will evaluate and report the onset date (and time, if applicable), resolution date (and time, if applicable), intensity, causality, action taken, seriousness criteria met (if applicable), and whether or not the subject discontinued the study as a result of the event.

If possible, the outcome of any AE resulting in permanent discontinuation or that was present at the end of the study should be reported. Subjects experiencing AEs that cause interruption or discontinuation of investigational product and those experiencing AEs that are present at the last visit or early termination visit should receive follow-up as appropriate.

All SAEs must be reported to the sponsor/Apellis Safety by completing the SAE form within 24 hours of the investigator or their representative becoming aware of the event, whether or not the event is deemed treatment related. Completed SAE forms should be emailed to [contact].

AEs will be coded in accordance with the Medical Dictionary for Regulatory Activities (MedDRA). If known, the diagnosis of the underlying illness or disorder should be recorded, rather than its individual symptoms.

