3.5. Analysis Timing

The analysis of data from the Part A Controlled Portion of the study will be performed when all subjects have completed the Part A Controlled Portion or discontinued early and all corresponding data have been entered into the database, reviewed, cleaned, and finalized, and the Week 12 Analysis database locked. At that time, the primary analysis will be performed, which will include all efficacy and safety analyses for the Part A Controlled Portion. For Week 12 Analysis, all summary tables will be presented by randomized group.

The analysis of data from the Part A Non-Controlled Portion will be performed once all subjects have completed the Part A Non-Controlled Portion or discontinued early and all corresponding data have been entered into the database, reviewed, cleaned, and finalized, and the Week 52 Analysis database locked. For disposition, baseline summary, and efficacy analysis, tables will be presented similarly as Week 12 Analysis.

The table summaries for protocol deviations, concomitant medications, study drug exposure and compliance, as well as all AE summaries will be presented in 5 columns: (1) Group 1's Part A Controlled Portion results; (2) Group 1's Part A Non-Controlled Portion results; (3) Group 2's Part A Non-Controlled Portion results; (4) Part A Non-Controlled Portion results combined (in other words, combining columns 2 and 3); (5) for all results since Pegcetacoplan injection (in other words, combining columns 1 and 4). More details on the summary layout are provided in the separate table shell document.

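### The Week 52 column for results since pegcetacoplan injection can include untreated Group 2 time after Week 12, and Group 2's pre-dose period has no Week 52 column

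*SAP*

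**What the plan says.** SAP 3.5 gives the layout of the Week 52 tables: "The table summaries for protocol deviations, concomitant medications, study drug exposure and compliance, as well as all AE summaries will be presented in 5 columns". Columns 1 and 2 are Group 1's two portions. Group 2 enters through "3) Group 2's Part A Non-Controlled Portion results". The next column is "4) Part A Non-Controlled Portion results combined (in other words, combining columns 2 and 3", and the last is "5) for all results since Pegcetacoplan injection (in other words, combining columns 1 and 4". The section refers to a separate table shell document for further layout detail.

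The portion is defined by study week. Protocol 6.1 has "Noncontrolled portion: Weeks 13-52 of the study", and SAP 3 repeats it. Group 2's first dose follows a different clock. Footnote G of Protocol Table 1 puts the Week 12 biopsy between Weeks 12 and 14 and adds that "Group 2 subjects cannot begin pegcetacoplan administration until after the biopsy occurs". Under footnote B these subjects "receive their supply of pegcetacoplan at the next scheduled clinic visit (Visit 7 or 8) following their biopsies".

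For Group 2, SAP 7.1 and Protocol 12.4 count treatment-emergent events from randomization, and SAP 5.4 counts concomitant medications from Day 1. For the Week 12 Analysis, SAP 3.5 presents every summary table by randomized group.

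**The concern.** The label of column 5 and its formula describe different things. The label starts at first injection. The formula starts, for Group 2, at Week 13. A Group 2 subject whose first dose comes later than that contributes untreated time to columns 3, 4 and 5. Nothing in the SAP removes it: the event and medication definitions start at randomization or Day 1, and the visit windows in SAP 13.4 apply only to safety laboratory, vital sign and ECG data.

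The gap is not a random stretch of follow-up. Under footnote B a first dose at Visit 8 arises when the biopsy falls after Visit 7, so the biopsy and any early complications lie between Visit 7 and the first dose. A biopsy complication in an undosed control could then be tabulated as a result since injection.

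The layout also has no column for Group 2 before first dose. Those events are treatment-emergent under SAP 7.1, and the Safety Set in SAP 4.3 includes everyone randomized to Group 2. Yet the Week 52 event tables have nowhere to put them. A Group 2 subject who left before Week 13 would belong to the Safety Set and have events in no Week 52 column.

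**Working it through.** The plan states no figure to reproduce, so the check is column algebra and day counting.

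**Columns.** Column 4 = 2 + 3 and column 5 = 1 + 4, so column 5 = 1 + 2 + 3. Group 2 enters column 5 only through column 3, the calendar-defined portion.

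**Inputs.**
- Visit 7 is Day 84 and Visit 8 is Day 98, each with a window of 7 days either side (Protocol Table 1).
- First day of the Non-Controlled Portion, S: Day 85 if Week 12 ends on Day 84, or Day 91 if the windows in SAP 13.4 are borrowed.
- Up to 9 subjects in Group 1 and 3 in Group 2. Assumption: all are followed to Day 364.

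**Formulas.** With first dose on day F:
- untreated days inside columns 3-5 = max(0, F − S)
- treated days left outside column 5 = max(0, S − F)

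| First dose F | Untreated, S = 85 | Left out, S = 85 | Untreated, S = 91 | Left out, S = 91 |
|---|---|---|---|---|
| Day 84 (Visit 7, nominal) | 0 | 1 | 0 | 7 |
| Day 91 (latest Visit 7, earliest Visit 8) | 6 | 0 | 0 | 0 |
| Day 98 (Visit 8, nominal) | 13 | 0 | 7 | 0 |
| Day 105 (Visit 8, latest) | 20 | 0 | 14 | 0 |

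**Share of patient-time at the maximum, all three Group 2 subjects affected.**
- S = 85: Group 2's portion lasts 364 − 85 + 1 = 280 days. Column 5 holds 9 × 364 + 3 × 280 = 4,116 patient-days. Untreated: 3 × 20 = 60, or 60/4,116 = 1.5% of column 5 and 20/280 = 7.1% of column 3.
- S = 91: the portion lasts 274 days. Column 5 holds 9 × 364 + 3 × 274 = 4,098 patient-days. Untreated: 3 × 14 = 42, or 42/4,098 = 1.0% of column 5 and 14/274 = 5.1% of column 3.

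**Effect on counts.** One subject is 1/3 = 33% of column 3 and 1/12 = 8% of column 5. The row changes by that much only if the subject has no post-dose event in the same row.

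**Control time without a Week 52 column.** 3 × 84 = 252 patient-days, out of 12 × 364 = 4,368 in Part A (5.8%). If the Controlled Portion is taken to run to Day 90, it is 3 × 90 = 270 (6.2%).

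**The case against.** The best defence is that the SAP never states how an event, medication or deviation is assigned to a portion. The label of column 5 is itself a first-dose anchor, and the table shells, which are not available here, may apply it. The design text also says Group 2 begins treatment during the noncontrolled portion. Part of this stands: misattribution is possible under the written rule, not certain. But the written rule is a formula, and the formula does not match the label. If the shells use first dose, the SAP's own definition still needs correcting.

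The second defence is that the untreated comparator is reported. This is right as far as it goes. A reader might infer that Group 2's control period is lost from the safety reporting. It is not, because the Week 12 Analysis covers it by randomized group, and the adverse event listings include events whatever their timing. Leaving it out of column 5 is also correct. The narrower gap is that no other Week 52 column carries it, and the Week 12 tables do not repair the content of columns 3-5.

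Third, the amount of time is small and the study is descriptive, with at most 12 subjects. That stands, and it limits the weight of the point.

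Three further inferences are not supported:
- A reader might stretch the gap to a first dose at Visit 9. Footnote B and Protocol 9.2.3 provide only for Visit 7 or 8.
- A reader might extend the point to the tables of potentially clinically significant values. The five-column layout does not list them, and SAP 7.2 presents the laboratory ones by treatment group and overall.
- A reader might set Protocol 11.2 against column 5. That section says "Any events that occur prior to the start of dosing will be categorized as pretreatment events" and makes the category depend on the randomized group. Its conflict is with Protocol 12.4 and SAP 7.1, which start Group 2's treatment-emergent events at randomization. If 11.2 governed, pre-dose events would not enter the adverse event summaries at all, though medications and deviations could still be misplaced.

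**Conclusion.** The point holds in a limited form. As written, SAP 3.5 can place untreated Group 2 results in columns 3-5 when first dose falls after the start of the Non-Controlled Portion. At Visit 8 this is 13 days at the nominal date and at most 20 with a Day 85 start, or 7 and at most 14 with a Day 91 start. With a Visit 7 dose on Day 84 it is zero, and the error runs the other way: 1 or 7 treated days fall outside column 5.

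These figures rest on the visit windows in Protocol Table 1 and on an assumed start day, because the SAP does not fix one for events or medications. The patient-time shares also assume full enrolment and follow-up. At no more than about 1.5% of column 5, the time alone would not matter. What matters is that the gap can contain the biopsy, and that with three subjects a single event is visible in the table. The missing pre-dose column is a gap in the Week 52 presentation only. The correction is worth making before the Week 52 database lock.

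**What to change.** 1. In SAP 3.5, bound Group 2's columns by the date and time of that subject's first pegcetacoplan infusion, so that columns 3-5 hold only results on or after first dose. Untreated time in those columns is then zero by construction, and treated days from a Visit 7 dose are no longer left out.
2. Add a column to the Week 52 adverse event, concomitant medication and deviation tables for Group 2 from randomization to before first dose, and keep it outside column 5. Bring the table shells into line.
3. Separately, reconcile Protocol 11.2 with Protocol 12.4 and SAP 7.1 on whether Group 2 events before first dose are pretreatment or treatment-emergent.

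The cost is wording in the SAP and shells and slightly wider tables. No new data are needed, since SAP 5.5 already uses the first infusion date to compute treatment duration.

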4. STATISTICAL ANALYSIS SETS

4.1. Screened Set

The screened set includes all subjects who provide written informed consent.

This set will be used for the summary of analysis sets.

4.2. Intent-to-Treat Set

The intent-to-treat (ITT) set consists of all subjects who are randomized.

The ITT set will be used for the summary of demographics, baseline characteristics, subject disposition, and analysis of all efficacy data.

4.3. Safety Set

The safety set includes all subjects who receive at least 1 dose of pegcetacoplan, and subjects who are randomized into Group 2.

All safety analyses will be conducted using the safety set.

4.4. Pharmacokinetic Set

The PK set includes all subjects in the ITT set who receive pegcetacoplan and have at least 1 evaluable postdose PK measurement.

All PK analyses will be conducted using the PK set.

4.5. Pharmacodynamic Set

The PD set includes all subjects in the ITT set who had at least 1 evaluable postscreening PD measurement.

All PD analyses will be conducted using the PD set.

5. STUDY SUBJECTS

5.1. Disposition of Subjects

For summary of analysis sets, the number and percentage of subjects screened, who failed screening, and who were included in each of the analysis sets as specified in Section 4 will be summarized and listed using the Screened Set.

For summary of disposition, the number and percentage of subjects who were treated, who were ongoing with study treatment, who completed study treatment, who discontinued study treatment with a primary reason for discontinuation, who were still in the study, who completed the study, who withdrew from the study with a primary reason for withdrawal will be summarized and listed using the ITT set. This summary will be further separated by treatment phases and combined. Variables to be summarized within each treatment phase will be adjusted accordingly to reflect the specific treatment phase.

5.2. Demographic and Other Baseline Characteristics

The following baseline demographic characteristics will be summarized and listed using the ITT set: age at screening, age group(≤ 65 years vs > 65 years), sex, ethnicity, race, weight, height, BMI, blood pressure.

The following baseline disease characteristics will be summarized and listed using the ITT set: underlying disease (C3GN, DDD or IC-MPGN) based on screening biopsy, underlying disease per medical history, potential causes of C3G/IC-MPGN, disease manifestations, drusen, prior kidney transplant (Y/N), time since last kidney transplant, total number of kidney transplants, prior dialysis (Y/N), baseline 24h uPCR, baseline uPCR (triplicate first-morning spot urine), baseline eGFR, baseline creatinine, baseline serum albumin, baseline serum C3, and time since post-transplant recurrence.

Time since last kidney transplant will be calculated as:

Time since last kidney transplant (years) = (Day 1 date – date of last kidney transplant)/365.25.

Time since post-transplant recurrence will be calculated as:

Time since post-transplant recurrence (years) = (Day 1 date – date of post-transplant recurrence)/365.25.

The following baseline biopsy characteristics will be summarized and listed using the ITT set: C3 staining, number of glomeruli, light microscopic patterns, Crescents (%), global sclerosis, interstitial fibrosis, tubular atrophy, total activity score, total chronicity score, and Banff score.

5.3. Medical History

Medical history will be coded using the latest MedDRA coding dictionary. For subjects in the Safety Set, medical history will be summarized by System Organ Class (SOC) and Preferred Term (PT) and listed. Each subject will be counted only once in each SOC or SOC/PT summary.

In the summary table, medical history will be presented by decreasing frequency of subjects overall within each SOC and then similarly by decreasing frequency of subjects overall within each PT. In cases of SOCs or PTs with equal frequencies, medical history will be sorted alphabetically.

Vaccination will be summarized for the Safety Set and listed. Kidney transplant history will be listed for the Safety Set.

Outputs in this section will also be provided using the ITT Set if the ITT set differs from the Safety Set.

5.4. Prior and Concomitant Medications

Prior and concomitant medications will be coded using the latest WHO Drug Dictionary version available. Summaries of prior and concomitant medications will be presented by ATC level 2 (therapeutic main group) and preferred term with numbers and percentages by treatment groups and overall for subjects in the Safety set. A subject who takes more than one medication will be counted only once if these medications belong to the same ATC level 2 classification.

In the summary tables, prior medications and concomitant medications will be presented by decreasing frequency of subjects overall within each ATC level 2 class and then similarly by decreasing frequency of subjects overall within each preferred term. In cases of ATC level 2 classes or preferred terms with equal frequencies, medications will be sorted alphabetically.

Prior medications are defined as those medications started prior to the administration of study drug for subjects in Group 1 or prior to Day 1 for subjects in Group 2. Concomitant medications are defined as those medications taken on/after the date of first administration of study drug for Group 1 subjects or on/after Day 1 for Group 2 subjects. Hence medications started before receiving study drug (or Day 1 for Group 2 subjects) but continuing after will be considered as both prior and concomitant medications. The listing of medications will identify prior and concomitant medications.

Outputs in this section will also be provided using the ITT Set if the ITT Set differs from the Safety Set.

